9.0 ADVERSE EVENTS

We will assess adverse outcomes in the perioperative period (the day of surgery until 6 weeks following surgery) as well as each study visit for 3 years after the procedure. We will ask the treating gynecologist about adverse events within 6 weeks of surgery. After 6 weeks when the participants may not have regular contact with the gynecologist, we will query study participants directly about adverse events.

We will list the known potential adverse events following Radiofrequency ablation treatment and ask for a yes/no response to determine whether it occurred. In addition, we will evaluate potential unknown adverse events by ask the treating gynecologists the following question "Have there been any adverse outcomes associated with the Radiofrequency ablation treatment that are not listed in this form?" Study participants will be asked "Have there been any negative changes in your health since your last study visit?"

Each reported adverse event will have a case report form that documents further details related to the adverse event including when it occurred, how it was diagnosed and treated, and the final clinical outcome.

Potential adverse events related to undergoing Radiofrequency ablation to be reported by the treating gynecologist within 6 weeks of surgery are:

1. Intraoperative injury to genitourinary or gastrointestinal tract, or other abdominal or pelvic organs
2. Blood transfusion
3. Unplanned visit to the Emergency Room or admission to the hospital
4. Pulmonary embolus or deep vein thrombosis
5. Major nerve injury with sensory or motor deficits
6. Infection at the site of the skin incision
7. Infection of the uterus or fibroid
8. Urinary tract infection
9. Hematoma at the site of trochar placement
10. Hernia at the site of trochar placement

11. Skin burn at the site of dispersive pad on bilateral thighs
12. New onset pelvic pain that persists >6 weeks after Radiofrequency ablation procedure

Potential adverse events related to undergoing Radiofrequency ablation to be reported by study participants from 6 weeks to 3 months after surgery are:

1. Hernia at the site of trochar placement
2. New onset pelvic pain

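### Section 9.0 asks for pelvic pain persisting beyond 6 weeks on a list that closes at 6 weeks, and its named participant events stop at 3 months although assessment is promised for 3 years

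*Combined protocol and SAP*

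**What the plan says.** Section 9.0 of the combined protocol and SAP says that adverse outcomes are assessed from the day of surgery to 6 weeks, "as well as each study visit for 3 years after the procedure". The reporter changes at week 6. Before then: "We will ask the treating gynecologist about adverse events within 6 weeks of surgery". After then: "we will query study participants directly about adverse events", with no end date in that sentence. Known potential events are put as yes/no items. An open question is added; for participants it asks whether their health has changed for the worse since the last study visit.

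Two named lists follow.

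- The gynecologist's list has 12 items and is headed as events "to be reported by the treating gynecologist within 6 weeks of surgery". Item 12 is "New onset pelvic pain that persists >6 weeks after Radiofrequency ablation procedure".
- The participant list has two items, trocar-site hernia and new-onset pelvic pain, and is headed as events "to be reported by study participants from 6 weeks to 3 months after surgery".

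Section 8.1.C names adverse events as a long-term outcome without saying what is asked. Table 2 in Section 8.1.D schedules the long-term outcomes at months 3, 6, 12, 18, 24, 30 and 36. It shows one in-person visit after the day of surgery, at 6 weeks.

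**The concern.** The section conflicts with itself twice. An event defined by what happens after week 6 is assigned to a reporter whose window ends at week 6. And a promise of 3 years of assessment is followed by a named participant list that ends at 3 months.

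The stake is how well persistent pain and late hernia are ascertained. Short-term operative morbidity is a secondary objective in Section 4.0, and the data and safety monitoring board reviews the Section 9.0 events at every meeting (Section 10.0). The first primary goal is to produce procedures that serve as a template for later comparative trials, so a defect in these forms could be carried into the randomized comparison with myomectomy, where lower operative morbidity is one of the advantages to be tested (Section 2.0).

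**Working it through.** The plan gives no figure on this point to reproduce. The check compares reporting windows and counts contacts.

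**1. Item 12 against its own window.** The gynecologist's window runs from week 0 to week 6. Item 12 can be read in two ways.

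- Pain still present more than 6 weeks after the procedure: it can be established only after week 6.
- Pain lasting more than 6 weeks from its onset in week *s*: it can be established only after week *s* + 6, which is never earlier than week 6.

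On either reading, the time at which the item can be confirmed does not overlap the window in which it is to be reported.

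**2. One case followed through the forms.** Suppose pain starts in week 2 and continues unchanged.

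| Contact | What is asked | Does the case fit? |
|---|---|---|
| Gynecologist, up to week 6 | Pain persisting beyond 6 weeks | Not yet. On the duration reading it qualifies only after week 2 + 6 = 8 |
| Participant, month 3 | New-onset pelvic pain, under a heading of 6 weeks to 3 months | Unclear. It is new relative to the procedure, but not new in that interval |
| Participant, each visit | Open question on change since the last visit | Unclear. Unchanged pain is not a change |
| Participant, months 6 to 36 | No named pain item | Only if she volunteers it |

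None of the symptom questionnaires, as Section 8.1.A describes them, is said to record pelvic pain that began after the procedure.

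**3. Could existing contacts close the gap?** Month 3 is about 3 × 52/12 = 13 weeks. Pain starting just before week 6 passes 6 weeks' duration at about week 6 + 6 = 12, so the month-3 contact could settle persistence for all pain that began before week 6. Pain starting after about week 13 − 6 = 7 cannot be called persistent at month 3 on the duration reading. It falls to month 6, where nothing named is asked.

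**4. Coverage of the named participant list.** Contacts after week 6: 7. Contacts inside the list's window: 1 (month 3). Contacts outside it: 7 − 1 = 6. Follow-up time after the list ends: 36 − 3 = 33 months, and 33/36 = 91.7% of the 36 months.

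**5. Size of any under-count.** This would need the true rates of persistent pain and late hernia, and the share of cases volunteered in reply to an open question. The documents give neither, so no figure is offered.

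**The case against.** The strongest reply is that collection never stops. Section 9.0 covers each visit for 3 years, participants are queried after week 6 without an end date, the open question is asked, every reported event gets a case report form, and Table 2 schedules long-term outcomes to month 36. All of this stands. A reader might infer that adverse-event collection ends at 3 months, or that late harms are bound to be under-counted. The documents support neither. What ends is the named prompt.

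A second reply is that item 12 itself uses new onset for pain arising after the procedure. On that usage, pain from week 2 still present at month 3 fits the participant item. This stands in part: the wording is ambiguous, not a proven blind spot. It follows that a reader should not infer that the forms must return zero cases of persistent pain. The month-3 item may catch some. But capture then depends on how each woman reads the item, and nothing in Section 9.0 says that onset before week 6 counts.

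Third, a reader might infer that clinic and hospital visits go unrecorded. They do not: Table 1 collects those related to surgery or fibroid symptoms within 6 weeks, and Section 12.0 reports hospitalizations and unplanned visits. Nor do the documents show that early events are missed because the gynecologist reports them. Table 1 includes adverse events among the perioperative outcomes, which Table 2 schedules at 2 days and at 1, 3 and 6 weeks.

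Last, the 3-month heading may be a slip for 3 years. The documents do not settle this. Either way, the heading and the opening of Section 9.0 must be reconciled.

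**Conclusion.** Both contradictions are real and rest only on the wording of Section 9.0. Item 12 cannot be confirmed within its own reporting window, and pain that starts before week 6 and continues has no item that clearly captures it. From month 6 to month 36, 6 of the 7 long-term contacts carry no named adverse event and rely on an unprompted question.

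The consequence is a risk of lower and less uniform capture of persistent pelvic pain and late hernia. That is a judgment about prompted against unprompted questions, and its size cannot be computed from the documents. It also assumes that the forms follow Section 9.0 as written. The point should be corrected because onset and persistence are hard to reconstruct at later visits.

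**What to change.** - On the 6-week gynecologist form, replace item 12 with an item for pelvic pain of new onset since the procedure, with its onset date. This keeps a pelvic pain prompt at the only in-person visit after the day of surgery.
- Record persistence at the contacts after week 6 with a participant item such as: *pelvic pain that began after the procedure, whenever it started, and lasted more than 6 weeks*. Collect the onset date and whether the pain is ongoing, so that either reading of item 12 can be derived, and state which reading will be reported.
- Reconcile the 3-month heading with the 3-year assessment by asking the hernia and pelvic pain items at every questionnaire from month 3 to month 36. State in Section 8.1.C or Table 2 that these named items form part of the long-term adverse-event outcome.

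The cost is form wording and a short protocol amendment, with no new visits. The downside is a few more questions per questionnaire and a possibly higher reported event rate.

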9.1 Adverse Event Grading Scale

Adverse events will be graded using the NCI Common Terminology Criteria for Adverse Events (CTCAE) and Common Toxicity Criteria (CTC), version 4. Using this system, adverse events are classified as follows:

Grade 1	Mild; asymptomatic or mild symptoms; clinical or diagnostic observations only; intervention not indicated.
Grade 2	Moderate; minimal, local or noninvasive intervention indicated; limiting age-appropriate instrumental activities of daily living
Grade 3	Severe or medically significant but not immediately life-threatening; hospitalization or prolongation of hospitalization indicated; disabling; limiting self care activities of daily living
Grade 4	Life-threatening consequences; urgent intervention indicated.
Grade 5	Death related to Adverse Event

9.2 Reporting of Adverse Events

Grade 4 or 5 adverse events will be reported to the respective institution's Institutional Review Board (IRB) and the UCSF Coordinating Center within 24 hours. The UCSF Coordinating Center will notify the study sponsor, the UCSF IRB, and the Data and Safety Monitoring Board (DSMB) Chair within 24 hours of the adverse event. The DSMB will receive a report of all adverse events every 4 months, categorized with the appropriate severity grading. The DSMB report will include details of the adverse event as reported in the Adverse Event Case Report Form.

10.0 DATA AND SAFETY AND MONITORING PLAN

The Data and Safety and Monitoring Board will be an independent committee with members who are not employed by the University of California. The committee will consist of two academic obstetrician/gynecologist with expertise in clinical studies of gynecologic interventions and the conduct of clinical trials, and a biostatistician with expertise in clinical trials and interim monitoring.

The DSMB will be charged with overseeing participant safety and monitoring the scientific validity of the trial. Prior to initiating the study, the DSMB will review and approve the study protocol. The DSMB will meet in-person or by conference call every 4 months for the first year of the study or until all study participants are recruited. The DSMB will then meet annually during the remaining 3 years of the study. All DSMB meetings will consist of a closed session

with the 3 members of the DSMB and an open session that includes the Principal Investigator, Study Statistician, Study Project Director and clinical site Principal Investigators.

The DSMB will review the following outcomes during each meeting:

1. Recruitment and retention data including compliance with enrollment criteria, screening to enrollment ratio, dropout rate and reason for dropouts
2. Demographic data of study participants
3. Intraoperative and Immediate Postoperative Outcomes listed in Section 8.1.B.
4. Adverse Events as described in Section 9.0

The DSMB will make recommendations for protocol changes or amendments to the Principal Investigator and Steering Committee. The Principal Investigator will provide a written response to the DSMB within 2 weeks of the DSMB report. Full details of the DSMB are described in the ULTRA DSMB Charter.

11.0 Participant Remuneration

Study participants will be provided with small values of debit or gift cards for their time and commitment to the study as follows: \$20 at the Baseline Week 6, Month 3, Month 6, Month 12, Month 18, Month 24, Month 30, and Month 36 visits. Participants will also be paid for the cost of parking and transportation for study related activities.

12.0 STATISTICAL CONSIDERATIONS

The primary analyses will evaluate changes from baseline to 1, 3, 6, 12, 18, 24, 30, and 36 months after Radiofrequency ablation treatment in all patient-reported outcomes including scores for the UFS-QOL and other standardized symptom and quality of life questionnaires. We will use ANOVA to evaluate the overall differences among these multiple time points in change scores, adjusting for potential confounding factors and baseline values to increase power. We will test the normality assumption and use nonparametric alternative models if the normality assumption is violated. We will use paired t-tests to directly compare mean scores from baseline to all follow-up time points.

Additional Planned Analyses: Descriptive analysis of the following outcomes will be reported with proportions and standard deviations for categorical outcomes and means with standard deviations for continuous outcomes.

1. Operative Outcomes: We will report intraoperative and immediate and long-term postoperative outcomes as described in Section 8.1.B.
2. Treatment Failure: Treatment failure is defined as any additional treatment for fibroids after the Radiofrequency ablation procedure including medical management for fibroid-related symptoms, myomectomy, hysterectomy, uterine artery embolization, MR Guided Focused Ultrasound, endometrial ablation, dilation and curettage, or any new and emerging fibroid treatments.

3. Resource Utilization: Medical resource utilization is measured by the number of hospitalizations, unplanned physician or clinic visits, and missed days of work or usual activities due to Radiofrequency ablation treatment.
4. Pregnancy Outcomes: We will report the proportion of women who become pregnant following Radiofrequency ablation treatment among all study participants and among the subgroup of women who report that they are actively trying to become pregnant prior to undergoing Radiofrequency ablation. For women who do become pregnant during the study, we will report the proportion who undergo miscarriage, abortion, or live births. We will also report obstetrical and perinatal complications.

Sample Size Calculation: The sample size of 100 was selected to allow each site investigator to perform an adequate number of cases to become competent and comfortable with the Radiofrequency ablation Procedure in anticipation of conducting future comparative trials. Each investigator (n=10) will perform 10 procedures, the first 5 cases with Halt support staff in the operating room and the remaining 5 cases independently. After 10 cases, the investigator will have the appropriate expertise to conduct a comparative trial of Radiofrequency ablation without requiring a "run-in" period of training cases.

The sample size of 100 will also provide sufficient power to evaluate the efficacy of Radiofrequency ablation as measured by changes in the UFS-QOL score from baseline to 3, 6, 12, 24, and 36 months following the procedure. Prior studies of women who undergo Radiofrequency ablation have shown the standard deviation of the UFS-QOL to be 21.7. Assuming 5% type 1 error and 90% power, we will be able to detect a minimal change of 7.2 in the UFS-QOL. This is a clinically significant change because meaningful improvements in quality of life are generally felt to occur with a minimum 10 point change in the UFS-QOL from baseline.

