3.0 STUDY OVERVIEW

The ULTRA study is a single-arm trial of 100 premenopausal women with symptomatic uterine fibroids who undergo treatment with the Radiofrequency ablation device. We will evaluate changes in fibroid-related symptoms from pre-treatment values to 3, 6, 12, 18, 24, 30, and 36 months after Radiofrequency ablation. We will also assess operative outcomes including procedure duration, complications, blood loss, post-operative pain, and return to usual activities. We will determine long-term efficacy of Radiofrequency ablation by evaluating the rate of re-treatment for symptomatic fibroids after the Radiofrequency ablation procedure.

Study participants will be recruited at 5 sites within the UC Fibroid Network: UC Davis, UC Irvine, UC Los Angeles, UC San Diego, and UC San Francisco. UC San Francisco will serve as the Coordinating Center for the trial with oversight of all scientific and administrative aspects of the study. All study data will be stored securely in a HIPAA compliant, secure database monitored by the UC San Francisco Coordinating Center. A data safety and monitoring board will oversee participant safety and protection.

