8.0 MEASURED VARIABLES

8.1. Outcome Variables

Outcomes will be measured at baseline prior to the Radiofrequency ablation procedure and at multiple time points for 3 years after the Radiofrequency ablation procedure. Questionnaires will be administered to evaluate patient-reported fibroid symptoms, operative outcomes, adverse events, the rate of re-intervention for fibroid symptoms, and surgeon self-assessment of skill and satisfaction. In the following section, outcome measurements are described in detail.

8.1.A Questionnaires to Assess Symptoms

These are validated questionnaires to assess the change in symptoms over time following the Radiofrequency ablation procedure.

1. **Uterine Fibroid Symptom-Quality of Life (UFS-QOL):** The UFS-QOL is a standardized questionnaire to evaluate fibroid-specific symptoms including heavy bleeding and urinary and bowel symptoms as well as the impact of fibroid symptoms on quality of life.^{4,5} The UFS-QOL has been used widely in studies of uterine preserving fibroid treatments including trials of Uterine Artery Embolization and MR Guided Focused Ultrasound.
2. **SF-36:** The SF-36 is a widely used, validated questionnaire to assess overall quality of health.⁶ There are 2 primary domains: Mental Health and Physical Health. The SF-36 has been used in multiple studies of women's health for a wide range of conditions including heavy uterine bleeding and symptomatic fibroids.
3. **Menstrual Impact Questionnaire (MIQ):** The MIQ is a validated questionnaire to evaluate the impact of heavy menstrual bleeding on quality-of-life.⁷ The MIQ has been used in trials of heavy bleeding that includes women with uterine fibroids.
4. **Overall Treatment Effect:** The Overall Treatment Effect used for this study is modified from a validated questionnaire to determine changes in symptoms following a medical intervention.⁸ The OTE consists of three questions that query women about whether symptoms have improved or not since treatment. These questionnaires have been compared with measures from the UFS-QOL among gynecologic patients.⁹ Three additional questions are generally linked to the OTE to assess overall patient satisfaction with treatment. This 6 question adapted OTE has been used in prior studies of women undergoing the Radiofrequency ablation procedure.

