3. Pregnancy and pregnancy outcomes: Participants will report all known pregnancies following Radiofrequency ablation. For each pregnancy, we will query participants about whether the pregnancy resulted in a miscarriage, abortion, or continued pregnancy. For continued pregnancies, we will ask participants to report obstetric outcomes including gestational age at birth, mode of delivery (vaginal or cesarean), and complications (e.g. placenta previa, placental abruption, preeclampsia).

8.1.D Schedule of Outcome Assessment

Outcomes will be assessed at varying timepoints from before the Radiofrequency ablation procedure to 3 years following the procedure (Table 2). In-person study visits will occur prior to surgery at the Screening Visit (SV), on the day of surgery called the Baseline Visit (BV), and 6

weeks following surgery. All other follow-up data will be collected through mailed or on-line questionnaires, or phone interviews.

Table 2. Schedule of Outcome Assessment and Participant Renumeration													
	SV	BV	2 day	1 wk	3 wk	6 wk	3 mo	6 mo	12 mo	18 mo	24 mo	30 mo	36 mo
In person visit	X	X				X							
Questionnaires to Assess Symptoms	X			X		X	X	X	X	X	X	X	X
Perioperative Outcomes		X	X	X	X	X							
Long Term Operative Outcomes							X	X	X	X	X	X	X

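### The primary analysis lists a 1-month comparison that is not collected, asks for change scores on an outcome with no baseline, and sets no primary score, visit or multiplicity rule, so the stated 5% holds per comparison only.

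*Combined protocol and SAP*

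**What the plan says.** Section 12.0 defines the primary analyses as the "changes from baseline to 1, 3, 6, 12, 18, 24, 30, and 36 months after Radiofrequency ablation treatment in all patient-reported outcomes". Two kinds of test are planned. The first is an omnibus test: "We will use ANOVA to evaluate the overall differences among these multiple time points in change scores". The second is pairwise: "We will use paired t-tests to directly compare mean scores from baseline to all follow-up time points". No score or visit is singled out, and no multiplicity rule is given. Only the analyses listed afterwards as additional are called descriptive.

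The time points differ across the document:

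- Section 3.0 has changes "from pre-treatment values to 3, 6, 12, 18, 24, 30, and 36 months after Radiofrequency ablation".
- Section 4.0 describes assessment before treatment and then at six-month intervals for three years.
- Section 8.1.D ("Table 2. Schedule of Outcome Assessment and Participant Renumeration") marks symptom questionnaires at screening, 1 week, 6 weeks, 3 months, 6 months and every six months to 36 months. It has no 1-month column, and its 3-week column has no symptom questionnaire.
- Section 11.0 pays participants at baseline and at the "Week 6, Month 3, Month 6, Month 12, Month 18, Month 24, Month 30, and Month 36 visits", with no Month 1.
- The sample size text in section 12.0 refers to "changes in the UFS-QOL score from baseline to 3, 6, 12, 24, and 36 months following the procedure".

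Section 8.1.A says of one of the patient-reported outcomes: "The OTE consists of three questions that query women about whether symptoms have improved or not since treatment".

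**The concern.** Three parts of the primary analysis do not work as written. The 1-month comparison has no data. The Overall Treatment Effect is itself a report of change made after treatment, so there is no baseline value to subtract or to pair with. The 6-week questionnaire is collected but has no place in the numbered list.

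The other issue is error control. If all patient-reported outcomes at all listed times are primary and each is tested at 5%, the chance of at least one false positive across that family is well above 5%. With no score or visit named in advance, the result to be emphasised can be chosen after the data are seen. This matters beyond the study itself, because section 2.0 says its effect sizes and standard deviations will be used to size a later randomized trial.

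**Working it through.** **Inputs.** From section 12.0: N = 100, SD 21.7, type I error 5%, power 90%, detectable change 7.2, meaningful change 10 points. From section 8.1.A: five questionnaires. Two assumptions are mine: 21.7 is the SD of the change (the text does not say), and there is no dropout.

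**1. Reproducing the plan's figure.** For a two-sided paired test at one visit, detectable change = SD × (z for 97.5% + z for 90%) / √n = 21.7 × (1.960 + 1.282) / 10 = 7.03. The noncentral t gives 7.10. The plan states 7.2, and at 7.2 the power is 91.3% (z) or 90.8% (t). A one-sided test would give 6.35, which is further away. So the 5% and 90% fit a single two-sided paired comparison of one UFS-QOL score at one visit.

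**2. Counting the tests.** Counting one score each for UFS-QOL, MIQ and SHOW-Q, and two for SF-36 (mental and physical), gives 5 scores. This is a minimum, because section 8.1.A describes UFS-QOL as covering both symptoms and quality of life, and SHOW-Q as covering several domains. The Overall Treatment Effect is left out because no paired test of it can be run. Section 12.0 lists 8 times; without the uncollected month, 7 remain. The family is 5 × 7 = 35 tests.

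**3. Family-wise error with each test at 5%.** This is the chance of at least one false positive when no score truly changes.

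- Independent tests: 1 − 0.95^35 = 0.83. For one score at 7 times: 1 − 0.95^7 = 0.30.
- Correlated tests: simulated normal test statistics, two-sided at 1.96, with one correlation between scores and one between times. The documents give no correlations, so these are assumptions.

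| Correlation between scores | Correlation between times | 35 tests | One score, 7 times |
|---|---|---|---|
| 0.3 | 0.5 | 0.70 | 0.23 |
| 0.5 | 0.6 | about 0.59 | about 0.21 |
| 0.6 | 0.7 | about 0.49 | 0.18 |

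Higher correlations lower these values. With a single common correlation of 0.8 between all tests, the 35-test figure is about 0.27, still well above 0.05.

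**4. What strict control would cost.** With Bonferroni over 35 tests, α = 0.05/35 = 0.00143, and power (t) is 52% for 7.2 points and 90% for 10 points. Over 40 tests (5 × 8, if an eighth time is restored), α = 0.00125 and power is 50% for 7.2 and about 90% for 10. So the 10-point change that the plan calls meaningful remains detectable under the assumptions above.

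**The case against.** The strongest reply is that this is an uncontrolled pilot. Its stated goals are to build procedures and gather preliminary data, N was chosen first so that investigators could be trained, and no success criterion depends on a p-value. Family-wise error is computed as if nothing changed, while section 1.0 reports symptom decreases of 52% and 56% in the pivotal trial. This stands, and it limits the consequence. It does not remove the point, because section 12.0 also claims enough power to evaluate efficacy and plans its primary analyses as tests.

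Several smaller replies also hold. Section 3.0's list is a subset of Table 2, section 4.0 is a summary, and the sample size text may simply name the visits it addresses. Only the 1-month entry names a time with no collection. The 6-week questionnaire is off the numbered list, but the paired t-test sentence refers to all follow-up time points and could include it. The Overall Treatment Effect problem adds nothing to the error rate.

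A reader might infer that the 5% belongs to no defined test. The documents do not support that. The sample size text ties it to UFS-QOL change, section 12.0 names the paired t-test, and together they give 7.03 to 7.10 against the stated 7.2. A reader might also take the 1-month entry to be the 6-week visit. That is plausible, but no section says so. Nor should 40 tests (87% if independent) be quoted for the plan as it stands, since that count includes the month with no data.

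**Conclusion.** The point holds, with moderate consequence. As written, the 1-month comparison and the change-score analysis of the Overall Treatment Effect cannot be carried out, and the standing of the 6-week questionnaire is unclear. The 5% is a per-comparison level for one UFS-QOL paired test with scale, visit and sidedness left open. It does not control error over the family that section 12.0 calls primary.

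Over the 35 tests that can be run, that error is 83% under independence and about 49% to 70% under the assumed correlations. For one UFS-QOL score at 7 times it is about 18% to 23% under the same assumptions. The direction is secure, but the exact size depends on correlations that the documents do not give.

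It would go too far to infer that the study is underpowered or that its findings would probably be false. Power for a 10-point change survives even strict correction, if 21.7 is the SD of change and nobody drops out.

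**What to change.** - Reconcile the time points in sections 3.0, 4.0, 8.1.D and 12.0 (including the sample size text) and use one list throughout. The sponsor should confirm whether the 1-month entry means the 6-week assessment and, if not, remove it or explain it.
- Name one UFS-QOL scale at one visit as the primary test at two-sided 5%, or a prespecified fixed sequence of visits chosen by the sponsor. State which scale the SD of 21.7 describes and whether it is an SD of change.
- Report the other scores and times as estimates with 95% confidence intervals.
- Report the Overall Treatment Effect as proportions with exact confidence intervals.

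The cost is protocol and SAP wording; no participants or visits are added. For one prespecified test the detectable change stays at about 7.1 points. The downside is that the other scores and visits would no longer support confirmatory claims.
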